### 3. OBJECTIVES

The purpose of this study is to evaluate the efficacy, safety, and PK of Klg10 in patients with PID in accordance both with FDA and EMA guidelines as specified previously.

#### 3.1 PRIMARY OBJECTIVES

##### Primary Efficacy Objective

To assess the efficacy of Klg10 administered to patients with PID to demonstrate that the rate of acute serious bacterial infections (i.e., the mean number of acute serious bacterial infections per patient-year) is less than 1.0 to provide substantial evidence of efficacy from day 1 to week 51/52.

##### Safety Objective

To assess the safety of Klg10 in the overall study population from day 1 to week 51/52.

##### Pharmacokinetic Objectives

To assess the distribution, metabolism, and elimination of Klg10, total IgG, IgG subclasses, and antigen-specific IgGs at steady state in 20 adult PID patients with different dosing schedules.

To evaluate trough concentrations of total IgG and compare to IVIg trough concentrations prior to the study entry.

#### 3.2 SECONDARY OBJECTIVES

##### Secondary Efficacy Objectives

To assess the efficacy of Klg10 administered to patients with PID as measured by:

1. IgG trough levels before each infusion and at the study termination visit (week 51/52).
2. IgG subclasses levels (IgG1, IgG2, IgG3, IgG4) before infusions 1, 5, 9, and 13 for the 28-day infusion schedule and at infusions 1, 7, 11, and 17 for the 21-day infusion schedule.
3. Anti-tetanus toxoid, anti-pneumococcal capsular polysaccharide, anti-Haemophilus influenza, and anti-measles antibodies levels before infusions 1, 5, 9, and 13 for the 28-day infusion schedule and before infusions 1, 7, 11, and 17 for the 21-day infusion schedule.

4. Occurrence and duration of any infection other than acute serious bacterial infections, from day 1 to week 51/52.
5. Occurrence and length of fever episodes, from day 1 to week 51/52.
6. Occurrence and duration of overall hospitalization, from day 1 to week 51/52.
7. Occurrence and duration of hospitalization due to infection, from day 1 to week 51/52.
8. Occurrence and duration of patients on antibiotics for the treatment of any kind of infections, from day 1 to week 51/52.
9. The missed days of work/school/other major activities due to infections, from day 1 to week 51/52.
10. Quality of life using the PedsQL™ questionnaires collected at baseline, at 24 weeks (infusion 7 for the 28-day schedule and infusion 9 for the 21-day schedule), and at the study termination visit.

CCI

## 4. STUDY DESIGN

### 4.1 OVERVIEW OF STUDY DESIGN

This is a phase III, open-label, prospective, single arm, historically controlled, multicenter study to evaluate efficacy, safety and PK of Klg10 in patients, aged 2 to 70 years at the time of screening and affected by PID.

However, enrollment of the 2 to 11 year-old pediatric patients will be delayed until acceptable safety and efficacy of Klg10 for the PID treatment of adolescents (age 12 to 17) or adults are demonstrated.

All patients will receive an intravenous infusion of Klg10 every 21 or 28 days (depending on the treatment regimen determined by their attending physician) for a period of 48 weeks at the study site. The first infusion of Klg10 will mark the beginning of the investigation period and enrollment, which is further described in Section 6.4. Visits will be performed every 21 ( $\pm$  3) days or 28 ( $\pm$  4) days after each infusion until week 51, or 52 (i.e., study termination visit), depending on the patient's treatment schedule (please refer to the table below).

Procedure 28-day regimen (21-day regimen in parentheses)	Timing	Comments
Screening	Day -28 to day 0 (Day -21 to day 0)	Up to 3 to 4 weeks prior to the first infusion
Infusion 1	Week 1, Day 1 Baseline	Enrollment
Infusion 2 to 4 (Infusion 2 to 4)	Week 4 to 12 (Week 3 to 9)	
PK assessment	Infusion 5, Week 16 (Infusion 7, Week 18)	For PK Evaluation Set only
Infusion 6 to 13 (Infusion 6 to 17)	Week 20 to 48 (Week 15 to 48)	
Study termination visit: 28 days after last infusion (21 days after last infusion)	Week 52 (Week 51)	Up to 3 to 4 weeks after the last study infusion

After obtaining a signed informed consent form (ICF), assent form (as applicable), and authorization to access personal health information, the screening procedures will be performed. Screening will include documentation of diagnosis by the site Investigator.

A Patient Diary will be given to patients at each infusion visit to record AEs, any medication taken including antibiotic treatment, infections of any type, fever episodes, days of hospitalizations, and days missed from major activities due to infections.

General and specific disease state questionnaires will be administered to patients to evaluate QoL.

Health care utilization data will also be collected during the study.

Patient personal satisfaction with participation and treatment during the study will be assessed.

The study design is in compliance with both FDA and EMA guidance as specified previously, except for the pediatric enrollment being lower than that required by FDA and EMA for market approval.

## **4.2 STUDY PERIOD**

Each patient should expect to participate in the study for approximately 13 months from the time of signing informed consent through the last study visit, including a 21- or 28-day screening period, a 48-week treatment period, and 3- or 4-week study termination visit (depending on the treatment regimen).

## **4.3 BLINDING AND RANDOMIZATION PROCEDURES**

This is an open-label study; no blinding and randomization procedures will be applied.

## **4.4 DATA COLLECTION**

### **4.4.1 DATA COLLECTED FROM PATIENTS**

The following data will be collected from each patient during their study participation:

- Medical history, including infections history, tolerance of previous IgG treatment, antibody response to pneumococcal vaccination (when available), and documentation of the last 3 commercially available IVIg infusions before the study entry.

NOTE that any potential undesirable effect from screening to infusion 1 will be reported as medical history. Those effects considered serious and related to prior IVIg, will also be notified to the marketing authorization holder.

- Demographic information including date of birth, gender, and ethnicity.
- Physical examination (evaluation of all body systems and body weight).
- Vital signs (blood pressure, heart rate, and temperature).
- Adverse events.
- Relevant prior and concomitant medications, including antibiotic treatment.
- Days missed from work/school/other major activities due to an infection.
- Fever episodes.
- Hospitalizations.
- Chest X-ray obtained within 6 months prior to enrollment.
- Laboratory analysis including hematology, blood chemistry, urinalysis, and intravascular hemolysis testing.
- Pregnancy test on urine (only for females of childbearing age).
- IgG levels throughout the study, and 2 documented IgG levels within 12 months (1 being within 6 months) prior to enrollment.
- IgG subclasses levels (IgG1, IgG2, IgG3, IgG4).
- Specific antibodies levels (anti-tetanus toxoid, anti-pneumococcal polysaccharide, anti-measles, and anti-haemophilus influenza).
- PK parameters of total IgG and specific antibodies (anti-tetanus toxoid, anti-pneumococcal polysaccharide, and anti-haemophilus influenza) (PK Evaluation Set only).
- QoL questionnaires (PedsQL™ and CCI ).
- Health care utilization data as measured by the need for any care in addition to the protocol-defined standard of care visits and items listed in the Schedule of Events (e.g., additional visits to health clinic, doctor office, urgent care center, hospital; additional prescription medications; additional therapies, etc).
- Study-specific questionnaire to evaluate patient satisfaction with participation and treatment during the study (Appendix A).

#### 4.4.2 TOOLS USED FOR DATA COLLECTION

Data will be recorded in medical records and Patient Diary, and collected on electronic case report form (eCRF).

##### **Patient Diary**

Patients, and/or patient's parent(s)/legal guardian(s), will be given a Patient Diary at each infusion visit. The Investigator will explain that the diary is a very important study document and that entries should be made daily in order to collect all safety and efficacy data. The Investigator will train the patient and/or patient's parent(s)/legal guardian(s) on how to complete the Patient Diary, starting at the first infusion visit. The Patient Diary will be collected at the following visit, data will be reviewed by the Investigator, and a new Patient Diary provided to patients at every visit. The patient/patient's parent(s)/legal guardian(s) will enter the following information in the diary:

- All AEs that occurred since the previous study infusion with special emphasis on AEs during the first 24 and 72 hours after infusion, and infections of any type as diagnosed by a physician or other qualified personnel.

NOTE: Infusion AEs during the infusion and within 1 hour after the infusion will be collected at the site, not at home with the Patient Diary.

- Any medication taken, prescription and non-prescription, including antibiotic treatment.
- Days missed from work/school/other major activities due to an infection.
- Fever episodes.
- Days of hospitalization.

The Patient Diary will be collected and reviewed by the Investigator at the clinic visit. Any additional information will be recorded on the source document and collected in the eCRF.

The following additional rules apply to documentation of safety information collected in the Patient Diary:

1. No corrections or additions to the Patient Diary will be allowed after it is reviewed by the site study staff.
2. Any blank or illegible fields on the Patient Diary must be described as missing in the eCRF.

3. Any corrections to the Patient Diary must be performed by the person completing the Patient Diary and should include a single strike through line through the incorrect value or text with a brief explanation for each change, the initials of that person, and date of correction.

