#### 5.1 INCLUSION CRITERIA

Patients must meet the following inclusion criteria to be enrolled into the study:

1. Written informed consent/assent obtained from patients/patients' parent(s) or legally acceptable representative indicating that they understand the purpose of and procedures required for the study and are willing to participate in it.
2. Confirmed clinical diagnosis of a PID as defined by 2017 International Union of Immunological Societies (IUIS) Phenotypic Classification for Primary Immunodeficiencies (Bousfiha A, 2018) and requiring treatment with IVIg. Documented agammaglobulinemia (defined as the total absence of one or more

classes of antibodies) or hypogammaglobulinemia (defined as low levels of one or more classes [ie, at least 2 standard deviations under the mean level per age]).

3. Male or female, ages 2 to 70 years at screening.
4. Received 200 to 800 mg/kg of a commercially available IVIg therapy in a range of 21- or 28-day intervals ( $\pm 3$  days or  $\pm 4$  days, respectively) for at least 3 infusion cycles prior to screening.  
(NOTE: Other IVIGs will be prohibited after ICF signature and until study end, week 51/52).
5. At least 2 documented IgG trough levels while receiving an IVIg, of  $\geq 6$  g/L obtained at 2 infusion cycles within 12 months (1 must be within 6 months) prior to ICF signature.
6. Patient (and parent/guardian where applicable) is willing to comply with all requirements of the protocol.
7. Females of child-bearing potential with a negative urine pregnancy test and who agree to employ adequate birth control measures during the study.
8. Authorization to access personal health information.
9. Patients previously participating in a clinical trial with another experimental IVIg may be enrolled if they have received stable commercially available IVIg therapy for at least 3 infusion cycles (21 or 28 days) prior to screening.
10. Patients currently on treatment with any subcutaneous immunoglobulin (SCIG) can be enrolled if they are switched to stable commercially available IVIg therapy for at least 3 infusion cycles (21 or 28 days) prior to screening.

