#### **7.1.2 SPECIAL WARNINGS AND PRECAUTIONS FOR USE**

Specific information regarding warnings, precautions, contraindications, AEs, and other pertinent information on the investigational product that may impact

patient participation is provided in the Investigator's Brochure.

For intravenous application only.

Potential complications can often be avoided by ensuring that patients:

- are not sensitive to human normal Ig by initially injecting the product slowly (with regards to the infusion rate, relevant section of the study protocol must be strictly followed);
- are carefully monitored for any symptoms throughout the infusion period. In particular, patients naive to human normal Ig, patients switched from an alternative IVIg product or when there has been a long interval since the previous infusion should be monitored at the hospital during the first infusion and for the first hour after the first infusion, in order to detect potential adverse signs. All other patients should be observed for at least 20 minutes after administration.

In all patients, IVIg administration requires:

- adequate hydration prior to the initiation of the infusion of IVIg;
- monitoring of urine output;
- monitoring of serum creatinine levels;
- avoidance of concomitant use of loop diuretics.

In case of adverse reaction, either the rate of administration must be reduced or the infusion stopped. The treatment required depends on the nature and severity of the adverse reaction.

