### 8.2.1 VITAL SIGNS

The vital signs, including blood pressure, heart rate and temperature will be collected at each visit (including screening and study termination visit) and recorded in the eCRF.

Temperature method should be consistent throughout the study for any given patient.

All vital sign measurements will have an allowable window of  $\pm 5$  minutes. For each infusion, vital signs will be measured at rest at the following time points:

- 10 to 15 min pre-infusion;
- After start of infusion: 5 minutes before each increase of the infusion rate;
- 30 minutes after reaching the maximum infusion rate; every 60 minutes thereafter;
- Immediately after completion of the infusion.

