### **10.4.3 SAFETY ENDPOINTS**

#### **Definition**

1. Number of AEs (%) and proportion of patients experiencing at least 1 AE.
2. Number of SAEs (%) and proportion of patients experiencing at least 1 SAE.
3. Number of related infusion AEs (%) occurring during infusion or within 1, 24, and 72 hours after the end of infusion and proportion of patients experiencing at least 1 of such related infusion AE.

4. The proportion and number of Klg10 infusions for which the infusion rate is decreased due to AEs.
5. Number and proportion of infusions with 1 or more infusion (temporally-associated) AE.
6. Changes in vital signs, physical examinations, and safety laboratory tests (hematology, serum chemistry, and urinalysis).
7. The proportion and number of patients with a positive Coomb's test following the 5th infusion for the 28-day infusion schedule and the 7th infusion for the 21-day infusion schedule.
8. The proportion and number of patients with a positive urine hemosiderin test following the 5th infusion for the 28-day infusion schedule and the 7th infusion for the 21-day infusion schedule.
9. Plasma-free hemoglobin level following the 5th infusion for the 28-day infusion schedule and the 7th infusion for the 21-day infusion schedule.
10. Serum haptoglobin level following the 5th infusion for the 28-day infusion schedule and the 7th infusion for the 21-day infusion schedule.

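### From infusion 2 on, AEs that start between leaving the site and minute 60 have no contemporaneous source, because the diary note gives the first hour to the site while the stated minimum stay is 20 minutes

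*Protocol*

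**What the plan says.** **Who records first-hour AEs.** The note in Protocol section 4.4.2 (Patient Diary) says that infusion AEs arising during the infusion and "within 1 hour after the infusion will be collected at the site, not at home with the Patient Diary". It does not distinguish between infusions. The bullet above it has the patient enter all AEs since the previous infusion, so the note works as an exception to a broad rule.

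**How long patients stay.** Protocol section 7.1.2 says that certain patients "should be monitored at the hospital during the first infusion and for the first hour after the first infusion". The groups named include "patients switched from an alternative IVIg product". The section continues: "All other patients should be observed for at least 20 minutes after administration". Section 8.2.1 places the last scheduled vital signs of an infusion visit at this point: "Immediately after completion of the infusion".

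**What the reminder call says.** Under Protocol section 6.8, a patient who mentions safety information on the day 2 or 3 call is reminded to write it in the diary. No exception is made for the first hour.

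**What the data feed.** Safety endpoint 3 in Protocol section 10.4.3 counts related infusion AEs "occurring during infusion or within 1, 24, and 72 hours after the end of infusion". The same section, with SAP section 10.1.2, declares safety if the upper one-sided 95% limit for the proportion of infusions with at least one temporally associated AE is below 0.4.

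**The concern.** The diary note works if the patient is still at the site at minute 60. From infusion 2 on, no stated rule ensures that. A patient who goes home at minute 20 and develops a headache at minute 40 is away from staff, and the note places the event outside the diary.

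Two things are at stake. The first is completeness: an AE that nobody records at the time may never be reported. The second is timing. SAP sections 6.2.13 and 6.2.23 measure the duration and onset of infusional AEs in hours from date and time, and SAP section 10.3.1 tabulates them by window. An event recalled weeks later may come without a clock time, and SAP section 6.3.2.1 has imputation rules for dates but none for times. Missed events can only lower the counts, so any error runs in the product's favour.

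**Working it through.** The plan states no figure for this point, so there is nothing to reproduce. The check compares the rules and then sets limits on the exposure.

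1. **Infusion 1.** Inclusion criterion 4 (Protocol section 5.1) requires at least 3 prior cycles "of a commercially available IVIg therapy in a range of 21- or 28-day intervals". Every enrolled patient is therefore switched from another product and falls under the one-hour rule. The first infusion has no gap.

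2. **Infusions 2 onward.** The one-hour rule refers to the first infusion. What remains is the minimum of 20 minutes. The longest possible gap is 60 − 20 = 40 minutes, or 40/60 = 67% of the hour, and it occurs only if the patient leaves at the minimum.

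3. **Infusions that could be affected.** Protocol Tables 1.1 and 1.2 give 13 and 17 infusions. The share after the first is 12/13 = 92% (28-day schedule) and 16/17 = 94% (21-day schedule).

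4. **Other routes for an AE at minute 40.**
   - AEs are recorded at every treatment visit (Protocol section 6.7); the next one is 3 or 4 weeks later.
   - An AE first described at diary review is entered as verbally reported (section 4.4.2, Case Report Forms, rule 3).
   - Safety information volunteered on the day 2 or 3 call goes to the source document, but the call is not meant to ask for it (section 6.8).
   - Patients are told to telephone the site about any symptom after treatment (section 9.2.6).
   - The eCRF accepts patient recall as an AE source (section 11.1).

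   Each route relies on memory or on the patient raising the matter. None sets out timed recording when the AE starts, and section 6.8 conflicts with the diary note.

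5. **Scale against the 0.4 criterion.** Assume 40 patients who each receive every infusion.
   - All on the 28-day schedule: 40 × 13 = 520 infusions, of which 40 × 12 = 480 could be affected. One infusion is 1/520 = 0.19 percentage points.
   - All on the 21-day schedule: 40 × 17 = 680 infusions, of which 40 × 16 = 640 could be affected. One infusion is 1/680 = 0.15 percentage points.
   - The raw Clopper-Pearson upper limit stays below 0.4 up to 189/520 = 36.3% (limit 0.3996) or 250/680 = 36.8% (limit 0.3992).
   - SAP section 10.1.2 multiplies this limit by the design effect, so a design effect above 1 would lower the permitted proportion.

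6. **What cannot be computed.** The documents give neither the rate of AEs starting in minutes 20 to 60 nor the times at which patients leave. Steps 2 and 3 measure clock time and infusions that could be affected. They do not measure missed AEs.

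**The case against.** The strongest reply is that the plan does provide for these events. The routes in step 4 exist, and rule 1 for the eCRF has the site enter every readable diary entry, so a minute-40 entry would be kept. The diary form is not among the documents, so what patients are actually told cannot be seen. All of this stands. A reader might infer that these AEs have no data source at all, or that patients are forbidden to report them; the documents support neither. What is missing is contemporaneous, timed recording.

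The 20-minute premise is also partly inference. It is a floor, it stands in a warnings section, and it is worded by patient rather than by infusion. Applying it to later infusions of switched patients is the natural reading but is not stated outright. A site that keeps patients for an hour satisfies both rules. Patients in the PK Evaluation Set have samples at 30 minutes and 2 hours after infusion 5 or 7 (Protocol section 8.4), so they are probably present for that hour at that infusion.

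Finally, an infusion counts once if it has any AE within 72 hours. It drops out of the 0.4 criterion only if its sole AE starts in the gap and no route ever picks it up. A reader might infer that the safety claim is materially biased. The documents show a direction but no amount.

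**Conclusion.** The point holds as a mismatch between Protocol sections 4.4.2, 6.8 and 7.1.2. From infusion 2 on, for a patient who leaves before minute 60, AEs starting between departure and minute 60 lack a contemporaneous source. The gap is at most 40 minutes per infusion, at no more than 12 of 13 or 16 of 17 infusions. Events missed there would lower the 1-hour summaries and the longer windows that contain that hour. They would lower the proportion tested against 0.4 only where the missed AE was the infusion's only one. The size of the effect is unknown.

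This rests on two assumptions: that the 20-minute minimum applies to later infusions, and that some patients leave before the hour is up. It justifies an inexpensive correction to data capture. It does not justify a claim that the safety conclusion is unsound.

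**What to change.** Reconcile Protocol sections 4.4.2, 6.8 and 7.1.2 for data capture:

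- Reword the diary note so that site staff record AEs until the patient leaves, and the patient records every AE that starts after leaving, including within the first hour, with clock time of onset.
- Bring the reminder-call wording into line with that note.
- Add the time of leaving the site to the eCRF.

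The SAP already works from AE start date and time for infusional AEs, so assigning the 1-, 24- and 72-hour windows from onset needs little or no change. The cost is one diary instruction with matching call wording and one eCRF field. The downside is that a few more minor AEs will be recorded. No change to observation time is proposed.

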### Case Report Forms

This study utilizes eCRFs to collect study-related data from each patient. A qualified and trained site staff member(s) is required to enter patient data in the eCRFs based on the medical information available in each patient's source record.

The following additional rules apply to documentation of Patient Diary information collected in the eCRFs:

1. The site must enter all readable entries in the Patient Diary into the eCRF.
2. Any illegible or implausible data (e.g., those values that may be biologically implausible - body temperature: 400°C) should be reviewed with the patient and parent(s)/legal guardian(s). If an AE is described upon review with the patient, this should be described in the source document and in the eCRF (e.g., if the patient above confirms body temperature of 40°C on the day in which body temperature: 400°C was written into his/her Patient Diary, this fever of 40°C should be recorded in the AE eCRF).
3. Any newly described safety information must not be written into the Patient Diary and must be described in the source document as a verbally reported AE. Any AE reported in this fashion must be entered on the eCRF.
4. Data should be entered into the eCRF within 72 hours following each patient's clinic visit or study procedure. Each patient's eCRF casebook will be compared with the patient's source records by a Sponsor-approved study monitor (or designee) over the duration of the study in order to ensure data collection accuracy.

